## Study design:

The design is a non-randomised stepped wedge trial, a type of controlled cluster cohort study in which the participants gradually move from control group to intervention group (Brown & Lilford, 2006; Copas et al., 2015). In this study, a cluster entail a whole clinic or a unit at a clinic and at the end of the study all clusters will have completed the intervention, i.e., participated in the education. Data will be collected for all participants both pre- and post-intervention. Figure 2 illustrates the study design, including time plan. The intervention was originally planned to be rolled out during four periods between September 2021 and June 2023 (figure 2) and an incomplete design was chosen, i.e., six periods are used, but every cluster is only included at four measurement points: at baseline, in conjunction with the education, at six months follow up and at twelve months follow up. Similar incomplete designs have been described previously (Copas et al., 2015; Karla Hemming, Lilford, & Girling, 2015). For practical reasons the primary care centres included in the first study period had to be included later than the hospital clinics, i.e., in December 2021. To avoid a data collection period during the summer vacation, their first follow up was conducted nine months post intervention. Thereafter they will fall into the same pattern of data collection at six months interval as the other clinics. The six months interval was chosen because it provides an intermediate (six months) and long-term (twelve months) follow up that allows for a reasonable evaluation of the effect of the education. The times of data collection is illustrated in figure 2.

One geriatric clinic (cluster 8) and one primary health care centres (cluster 9) who were included at baseline decided in 2023 not to participate in the study for logistic reasons, e.g., having to prioritize other training for the staff. Therefor another primary health care centre was included (new cluster 8) and one training day was also open to participants from various primary health care centres (new cluster 9). For these clusters there is therefore no baseline data available, only pre-intervention data. In addition, the data collection phase had to be prolonged until September 2023.

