## Measurements:

Self-reported measurements will be collected with the questionnaire REAGERA-P, which has previously been validated in a Swedish health care professional sample (J. Simmons, Wenemark, & Ludvigsson, 2021).

**Main outcome:** Potential effect of the training on participants asking older patients questions about abuse. This will be measured as self-reported number of times the professional has asked patients questions about abuse (range 0-10 and above). The answers will be analysed both as a dichotomous variable (never/ one or more times) and as a continuous variable.

**Secondary outcomes:** Secondary outcome measures are items in REAGERA-P about the four main learning objectives of the education (figure 1). Changes in all variables between the measurement points will be considered.

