### **Sample size**

Cluster sample size was calculated using the Shiny CRT Calculator web application (Karla Hemming, Kasza, Hooper, Forbes, & Taljaard, 2020). Significance level was set to 0.05 and power to 0.8. We planned for a three-step intervention and used the discrete time decay. Initially we had planned a complete four period stepped wedge design and hence, that was used in the sample size calculation together with the discrete time decay. Divergent cluster sizes were expected and coefficient of variation for a cluster size was set at 0.5. Results from a pilot study (Johanna Simmons, Motamed, Ludvigsson, & Swahnberg, 2022) was used to estimate cluster auto correlation at 0.6. Proportion

was set as outcome, and we used data from the pilot study to estimate the proportion under control at 0.26 and the proportion under intervention at 0.56. A cluster size of 10 then suffice to reach adequate power. Our smallest expected cluster has 31 participants and hence even with a response rate of less than 40% this is sufficient.

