## Statistical analysis

The background characteristics of participants will be explored using descriptive statistics and comparisons will be made between clusters to detect significant differences. Missing data will be analysed and, if appropriate, multiple imputations will be considered. Attrition analysis will be conducted using e.g., chi square test and student's t-test to detect differences between those lost to follow up and those retained.

In a stepped wedge trial, results are compared across unexposed and exposed observation periods in the clusters, similar to the control and intervention arm in a parallel cluster trial (K Hemming, Haines, Chilton, Girling, & Lilford, 2015). The primary effect of this study will hence be calculated by comparing the main outcome (propensity to ask questions about abuse) in all clusters pre-intervention with all clusters post-intervention. Both mean difference in reported frequency of asking questions and changes in proportion of participants that report ever having asked questions about abuse will be reported. For the continuous outcome a linear mixed effect model will be used and for the binary outcome a generalised linear mixed effect model. The models will consider repeated measures and include cluster as random effect to determine if the anticipated effect of the model is dependent on the cluster, i.e., unit or clinic. During a stepped wedge trial more and more clusters will gradually transition from unexposed to exposed status, meaning that observation in the exposed status will on average be of a later date than the unexposed observation (K Hemming et al., 2015). This may introduce a bias in the study considering that there may be underlying temporal trends affecting the outcome, e.g., an increasing awareness of elder abuse in society over time. Therefore, both intervention status and time will be included as fixed effects in the models. Also, models will be adjusted for covariates, e.g., background characteristics, significantly associated with the outcome.

[figure not shown]
We propose that the education will work by participants overcoming personal and organizational barriers towards asking older patients questions about abuse. The items in REAGERA-P used to evaluate the effect on the different barriers and facilitators are described in figure 1 and they will be included in linear models (for continuous outcome) and generalised linear models (for binary

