outcomes) to determine the effect of the intervention on these outcomes. If results support the theoretical model, efforts will be made to test if changes in perceived barriers mediate a potential effect of the intervention on the primary outcome, i.e., asking questions about abuse.

[figure not shown]
Data from the medical records will be retrieved for the following periods a) 6 months pre-intervention, b) 0-6 months post intervention and c) 6-12 months post intervention. A linear mixed effect model will be used to investigate changes concerning how many victims are identified pre- and post-intervention at the participating clinics.

In all models, we will strive for parsimony; analysis will therefore be performed to determine which variables to include in multivariate analysis and only covariates that significantly affect the model will be included. Assumptions for models will be assessed graphically and, if needed, bootstrapping will be used to ensure model robustness. Significance level will be set at  $p=0.05$  and results will be reported with 95% confidence intervals.

**Figure 1.** Theoretical model. An illustration of the alignment between learning activities (yellow), learning objective, that is, barriers and facilitators on a personal (green) and organisational (blue) level as well as evaluation (red). EA, elder abuse; REAGERA-P, Responding to Elder Abuse in GERiatric care—Provider questionnaire.

**Figure 2** Design of the study and data collection points. An incomplete stepped wedge trial is planned. All clusters are measured pre-intervention (yellow squares=baseline and in conjunction with the educational day) and post-intervention (blue squares=at 6–8 months and 12–14 months of follow-up). Time of intervention is denoted by the red contour.

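### With time adjusted for, the single pre/post term mainly estimates the first-follow-up effect, and no planned model for the main outcome separates the two follow-ups

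*Combined protocol and SAP*

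**What the plan says.** The Statistical analysis section describes the primary effect as "comparing the main outcome (propensity to ask questions about abuse) in all clusters pre-intervention with all clusters post-intervention". It uses a linear mixed model for the count and a generalised linear mixed model for the binary version, and in both "both intervention status and time will be included as fixed effects in the models". The coding of time is not given.

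Under Study design, "every cluster is only included at four measurement points": two before the effect can act (baseline and the education day) and two after. The six-month spacing is justified because "it provides an intermediate (six months) and long-term (twelve months) follow up".

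Three other places come near the question without answering it:
- Measurements, in the paragraph on secondary outcomes: "Changes in all variables between the measurement points will be considered". No model or contrast is named.
- Statistical analysis, last paragraph: "Assumptions for models will be assessed graphically". This is a general statement.
- The medical-record data are retrieved in two separate half-year windows after the education. That outcome is called experimental, and its model is again described as pre against post.

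No section states that the effect is assumed equal at both follow-ups, and none plans separate follow-up effects for the main outcome.

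**The concern.** A reader told that all pre-education data are compared with all post-education data would expect both follow-ups to count about equally. Once time is in the model they do not. A post-education survey tells us about the effect directly only if some cluster surveyed in the same period has not yet been educated. Later periods have few or no such clusters, and most second follow-ups fall there.

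If the effect is the same at both follow-ups, unequal weighting does no harm. If it fades or grows, the single estimate stands mostly for the first follow-up and could be read as evidence about lasting change. The design collects long-term data, so the analysis should say in advance how those data are used.

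**Working it through.** **Plan's own figure.** The only nearby figure is the cluster size of 10 under Sample size. The ICC and number of clusters behind it are not stated, so it cannot be reproduced. Assuming 9 clusters in the complete four-period, three-step design, size 10 gives power 0.97, 0.91, 0.84 and 0.78 at ICC 0.01, 0.05, 0.10 and 0.15. An ICC range of 0.01-0.10 is therefore compatible with the plan.

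**Layout (assumed, because Figure 2 is not shown).** Sample size says "We planned for a three-step intervention", while Study design says "rolled out during four periods between September 2021 and June 2023", so both were tried. The three-step layout has three clusters per step, baseline in period 1 and education in period 2, 3 or 4. It agrees with the Figure 2 note, which puts cluster 4's baseline in period 1 and its education in period 3.

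| Period | 1 | 2 | 3 | 4 | 5 | 6 |
|---|---|---|---|---|---|---|
| Step 1 | pre | pre | F1 | F2 | | |
| Step 2 | pre | | pre | F1 | F2 | |
| Step 3 | pre | | | pre | F1 | F2 |

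**Count.** First follow-ups (F1) with an unexposed cluster in the same period are those of steps 1 and 2: 3 + 3 = 6 of 9. For second follow-ups (F2) only step 1 qualifies: 3 of 9. With education in periods 1-4 and 2/2/2/3 clusters the counts are 6 and 4.

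**Weights.** By generalised least squares on cluster-period means, the coefficient is the last element of (Σ X'V⁻¹X)⁻¹ Σ X'V⁻¹ȳ, where X holds time and intervention status. V = ICC × R + ((1 - ICC)/m) × [(1 - ρ)I + ρJ], where R is the correlation of cluster effects over periods, m the cluster size and ρ the within-person correlation. Summing the coefficients over F1 and F2 cells gives w1 + w2 = 1, so the expected estimate is w1·δ1 + w2·δ2 for true effects δ1 and δ2.

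**One case in full.** Three steps, categorical time, 31 per cluster (the plan's smallest expected cluster), autocorrelation 0.6 with decay (Sample size), ICC 0.05 and ρ = 0.5 (both assumed):

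| Period | pre | F1 | F2 |
|---|---|---|---|
| 3 | -0.456 | +0.456 | |
| 4 | -0.544 | +0.544 | 0.000 |
| 5 | | +0.204 | -0.204 |
| 6 | | | 0.000 |

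w1 = 0.456 + 0.544 + 0.204 = 1.204 and w2 = -0.204. In period 5 every surveyed cluster is exposed, so the model sets first against second follow-ups there. The F2 cell alone in period 6 contributes nothing.

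**Range of w2:**

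| Setting | w2 |
|---|---|
| Three steps, 9 × 50, ICC 0.01-0.10 | -0.30 to +0.14 |
| Education in periods 1-4, same inputs | -0.22 to +0.27 |
| ICC approaching 0 | up to about +0.38 |
| Random intervention effect by cluster | -0.44 to +0.24 |
| Three steps, wider grid (ICC to 0.20, uneven sizes, ρ to 0.7) | -0.49 to +0.20 |
| Periods 1-4, wider grid | -0.36 to +0.31 |
| Two late clusters without baseline, wider grid | -0.53 to +0.19 |

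Two variants went lower: -0.59 with one first-step cluster followed up late, and -0.65 with baseline one period before education, which disagrees with the Figure 2 note. These ranges are not bounds.

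**Against the observation share.** With equal response F2 is 0.50 of post-education observations. If F2 responders are 70% or 50% of F1 responders, the share is 0.7/1.7 = 0.41 or 0.5/1.5 = 0.33, and w2 is at most 0.32 or 0.26. It was below the share in every run.

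**Consequence (illustrative effects).** With δ1 = 0.30 and δ2 = 0.15 the expected estimate is 0.30 - 0.15·w2: 0.24 at w2 = +0.4, 0.30 at 0, 0.33 at -0.2 and 0.375 at -0.5. The simple average is 0.225. The last two estimates exceed both true effects.

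**Binary model (simulated).** With odds ratios of 3.62 (0.26 to 0.56) and then 1.60 (0.26 to 0.36), the log-scale average is √(3.62 × 1.60) = 2.41. The single term gave 3.5-4.5 with three steps, 3.0-3.7 with periods 1-4, and as low as 2.8 at ICC near 0. Separate terms returned 3.6-3.7 and 1.55-1.67.

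**Coding of time.** If time meant measurement occasion, intervention status would be the sum of the two follow-up indicators and could not be estimated (rank 4 of 5). Calendar period must be meant.

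**The case against.** The strongest reply is that the harm is hypothetical. A single intervention term with time adjustment is a standard stepped-wedge model, no section predicts a changing effect, and the plan promises only a pre/post effect. At the favourable end the difference is small: a 0.30 effect fading to 0.10 with weight 0.38 is estimated at 0.30 - 0.20 × 0.38 = 0.22, against an average of 0.20. The layout is inferred, and the main ranges ignore the nine-month first follow-up of some centres. The sentence on changes between measurement points also shows an intention to look by time point.

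Much of this stands. The point is conditional, and the exact weights are unknown. What does not fall is the direction, which held in every layout tried, including those with a delayed follow-up. An intention stated for secondary outcomes, with no model, does not specify an analysis of the main outcome.

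Two stronger readings are tempting. A reader might infer that the primary analysis is biased as planned; the documents do not support that, since nothing in them says the effect will change. A reader might also infer that the sponsor intends to claim a twelve-month effect from the single term; no section says so.

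**Conclusion.** The point holds as a cheap improvement. The single term mainly reflects the first follow-up. The second follow-up's weight is about -0.5 to +0.4 in the main runs, often near or below zero, and always below its share of the data. This rests on an assumed layout, ICC and within-person correlation; the direction was the same throughout.

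If the effect is constant, this particular distortion is absent. That should not be stretched to say that the estimate is then unbiased: the trial is non-randomised, inclusion depends on attending the education, and some replacement clusters have no baseline survey. If the effect changes, the single estimate does not represent both follow-ups, and the plan has no pre-specified model for the main outcome that would reveal it.

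**What to change.** Keep the single-term model as primary, and make these changes to the Statistical analysis section:
- State that time is coded as calendar period.
- State that the single-term result assumes a constant effect and otherwise mainly reflects the first follow-up.
- Pre-specify a companion model, identical except for separate terms for first and second post-education follow-up. Report both effects and their difference with 95% confidence intervals.
- Rest any long-term statement on the second term only, labelled second follow-up (about 12-15 months). Centres first surveyed at nine months and then six months later reach 9 + 6 = 15 months.
- Add a sensitivity analysis by actual months since education.
- Note that with categorical time a second follow-up alone in the last period does not inform its term.

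The cost is one extra parameter and no new data. The second-follow-up standard error is about 1.2-1.8 times the first; in one case (31 per cluster, ICC 0.05) it is 0.170 against 0.120 SD units, a ratio of 1.4. The average of the two effects has a standard error about 2-47% above the single term's, and more if the random effects are misspecified. For estimating that average, the single term has the lower mean squared error when the effect changes by less than about 0.02-0.08, so replacing the primary is not requested.

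Power to detect a change of 0.20 between follow-ups (9 clusters of 50, SD 0.47, t with 7 df, no allowance for the nine-month delay) is at least 0.97 at ICC 0.01, 0.78-0.97 at 0.05 and 0.58-0.84 at 0.10. The plan should therefore say that a non-significant difference does not prove a constant effect.

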### 1. Awareness of elder abuse, sense of responsibility for identifying victims:

- Lack of awareness of elder abuse as a barrier towards identifying victims.
- Perceived responsibility of the health care services as well as different health care professions to identify victims of elder abuse
- Case vignette, measuring awareness and propensity for asking patients questions about abuse.

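### The models named for the aim 2 barrier and facilitator items carry no stated cluster, participant or time term, and copying the main-outcome model would not fully repair this

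*Combined protocol and SAP*

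**What the plan says.** For the main outcome, the Statistical analysis section specifies a linear mixed model (continuous version) and a generalised linear mixed model (binary version). It adds: "The models will consider repeated measures and include cluster as random effect". It explains that exposed observations fall later on average, that "there may be underlying temporal trends affecting the outcome", and gives as its example "an increasing awareness of elder abuse in society over time". It concludes: "Therefore, both intervention status and time will be included as fixed effects in the models".

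The next paragraph turns to the items for aim 2, which will be "included in linear models (for continuous outcome) and generalised linear models (for binary" outcomes), in order to estimate the intervention's effect on them. The word mixed is absent, and no cluster, participant or time term is given. The medical-records outcome, later in the same section, is again given a linear mixed model.

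Three other statements bear on this:
- Measurements says of the secondary outcomes: "Changes in all variables between the measurement points will be considered". It names no model.
- Study design says that "every cluster is only included at four measurement points", so the same staff can answer up to four times within a clinic.
- The first group of secondary outcomes includes "Lack of awareness of elder abuse as a barrier towards identifying victims".

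**The concern.** Aim 2 rests on these tests, and the conditional mediation step would start from them. The text leaves three analyses open:

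- **A, literal:** intervention status only, with independent errors.
- **B, time only:** time carries over because the plan says it enters the models in general; cluster and participant terms do not.
- **C, full:** the main-outcome model, taken as cluster and participant intercepts plus period.

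Under A, a calendar trend is counted as an effect of the education. The plan's own example of a trend is rising awareness, and awareness is an aim 2 construct. Under A and B, the standard errors ignore correlation within clinics and within persons. The choice among A, B and C could be made after the data are seen.

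**Working it through.** **Plan's own figures.** None is given for the aim 2 items. The cluster size of 10 in Sample size concerns the binary main outcome. The ICC and number of clusters behind it are not stated, so it cannot be uniquely reproduced, and this point does not depend on it.

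**Inputs from the documents.** Six periods and four measurements per cluster, two before and two after the education (Study design, Figure 2 caption); significance level 0.05 (two-sided assumed); cluster autocorrelation 0.6 with discrete-time decay (Sample size, given there for a proportion).

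**Assumptions.** Nine clusters, three educated in each of periods t = 2, 3, 4, each measured at periods 1, t (pre), t+1 and t+2 (post). Total variance is 1, within-person correlation 0.5, ICC 0.01 to 0.10, and m = 30 to 50 per cluster. Figure 2 is not shown, so other layouts were also tried.

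**1. Trend bias under A.** For education in period t, mean post minus mean pre period is (t + 1.5) − (1 + t)/2 = t/2 + 1, that is 2.0, 2.5 and 3.0; the average is 2.5. If two clusters in the last step lack baseline, the pre mean is 34/16 = 2.125 and the post mean 81/18 = 4.5, a gap of 2.4. Four-step layouts give 2.1 to 2.4. A trend of b per period therefore adds about 2.1 to 2.5b to the estimate.

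**2. A, no decay.** Model variance is 1/(9m). True variance is 0.5/(9m), because each person's post-minus-pre contrast has variance 1 − 0.5. Write R for true over model variance; with no bias, type I error is 2[1 − Φ(1.96/√R)]. Here R = 0.5, giving 2[1 − Φ(2.77)] = 0.6%.

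With an assumed trend of 0.03 SD per period the bias is 2.5 × 0.03 = 0.075 SD. At m = 30 the model SE is 1/√270 = 0.061, the critical value 0.119 and the true SE √(0.5/270) = 0.043. The false-positive rate is 1 − Φ((0.119 − 0.075)/0.043) = 15%; at m = 50 it reaches 31%. At 0.05 SD it is 55 to 84%, at 0.02 SD 5 to 10%, and at 0.01 SD 1.5 to 2.3%.

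**3. A, autocorrelation 0.6, no trend.** The clinic-level post-minus-pre contrast has variance ICC × 0.832, 0.827 and 0.824 for the three steps, mean 0.828. So R = 0.5 + 0.828(m − 1)ICC.
- m = 30, ICC 0.01: R = 0.74, type I error 2.3%.
- m = 31, ICC 0.02: R = 1.00, 5%.
- m = 50, ICC 0.10: R = 4.56, 36%.

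**4. B.** Once period is fitted, only periods 3 and 4 hold both exposed and unexposed clusters. Exposure, centred within period, is +1/2 and −1/2 (first and second step) in period 3, and +1/3, +1/3 and −2/3 in period 4. The between-period cross-products, +1/6 and −1/6, cancel. So neither decay nor within-person correlation matters, and R = 1 + (m − 1)ICC.
- m = 30, ICC 0.01: R = 1.29, about 8.5%.
- m = 50, ICC 0.10: R = 5.9, about 42%.

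**5. C.** This is generalised least squares with cluster and participant intercepts plus period; under decay its working variances are the best-fitting ones.

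| Type I error, no trend | No decay | Autocorrelation 0.6 |
|---|---|---|
| A | 0.6% | 2.3–36% |
| B | 8.5–42% | 8.5–42.4% |
| C | 5.0% | 8.3–42.4% |

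The 5.0% for C is built in, because the variances are treated as known and the model is then correct. Fitting C by REML to 500 simulated trials per cell gave 6.2 to 6.4% with no decay, and 26.6% with decay at ICC 0.05 and 40 per cluster (formula 25.4%).

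**6. Other layouts, no decay.** Four-step: A 0.7 to 4.9%, B 5.2 to 37%. Three-step with two clusters lacking baseline: A 0.8 to 2.7%.

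**The case against.** The strongest reply is that the wording is shorthand. The time adjustment is justified by a property of the whole stepped-wedge design, and "Therefore, both intervention status and time will be included as fixed effects in the models" can be read as covering every model. The plan gives its model terms once; the records paragraph does not repeat them either. This stands as far as it goes: the documents do not establish that an unadjusted analysis is intended. But carry-over of that sentence supplies only time, which is reading B. Mixed is used both before and after the aim 2 sentence but not in it. The bootstrap provision for all models is conditional and names no resampling unit.

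A second objection concerns the remedy, and it stands. A reader might infer that copying the main-outcome model restores 5% error. That holds only without decay. Under the one clinic-correlation figure in the documents, 0.6, B and C coincide, and A lies below both when there is no trend.

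Two other inferences go too far. One is that the literal model must give standard errors that are too small; the error runs in either direction. The other is that trend bias is certain: the plan says only that trends may exist, gives no size, and the bias arises only if time is left out. Small trends also produce few false positives under A.

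Finally, these are secondary outcomes and the mediation step is conditional. That limits the consequences, but aim 2 consists of these tests.

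**Conclusion.** The point holds as an unresolved specification whose literal form would give wrong results. Two conclusions need no particular parameter value. Without a time term, a common trend enters the effect estimate, at about 2.1 to 2.5 times the per-period trend in the layouts tried. With time but no cluster or participant terms, that bias goes but the tests are too liberal, at about 8.5 to 42% in the main layout. The direction of the error without a time term and without a trend is not fixed: about 0.6% with no decay, up to 36% with autocorrelation 0.6.

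The percentages are illustrative. They rest on assumed ICC, within-person correlation, cluster sizes and layout, and the 0.6 is borrowed from a calculation for a different outcome. The calibration gain from C over B depends on clinic correlation not decaying. The point should be settled before analysis; if mixed models were always intended, the aim 2 part is only a clarification.

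**What to change.** Reword the aim 2 sentence in Statistical analysis to say that these items are analysed with linear and generalised linear mixed models, with intervention status and period as fixed effects, cluster and participant as random effects, and any bootstrap resampling whole clusters.

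In the same revision, add a cluster-by-period random effect and a small-sample reference distribution, for the main outcome as well as the aim 2 items. The Sample size section assumes decaying clinic correlation, and cluster and participant intercepts plus time do not absorb it.

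The cost is a short text change and a little programming. Intervals will widen: with no decay and 30 per cluster, the true SE is about 0.084 to 0.087 SD under C against 0.043 under A, which buys its precision by giving no protection against a trend. With about nine clusters, the cluster-by-period variance will be imprecisely estimated.

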### **Other outcome measures:**

Anonymous data will be drawn from the medical records. It will consist of the number of time elder abuse have been recorded in the designated place in the digital medical record for each participating clinic. The validity of this data has not been established and it will therefore be considered an experimental outcome but could potentially be an objective assessment of whether the intervention leads to increased identification of patients subjected to elder abuse.

Some items in REAGERA-P does not directly measure any of the learning objectives of the education but could potentially be affected by the intervention and will hence also be considered. They are as follows:

- Proportion of respondents reporting that victims of elder abuse were given an adequate follow up.
- Proportion of respondents reporting suspecting elder abuse but refraining from asking questions.
- Proportion of respondents reporting changed working practice at follow up because of the education.

**Covariates** potentially affecting both the intervention effectiveness and the outcome will be considered. These include background characteristics of participants both on an individual and group level.

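### The medical-record windows cannot separate an effect that changes over time from a secular trend within clinics; the single pre/post effect is identified within clinics only if it is constant over 12 months

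*Combined protocol and SAP*

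**What the plan says.** The Statistical analysis section retrieves record data for "a) 6 months pre-intervention, b) 0-6 months post intervention and c) 6-12 months post intervention" and states: "A linear mixed effect model will be used to investigate changes concerning how many victims are identified pre- and post-intervention at the participating clinics". No records outside these windows are planned.

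Under Other outcome measures, the count is taken per participating clinic. It is labelled experimental because its validity is unknown, but the plan adds that it "could potentially be an objective assessment of whether the intervention leads to increased identification of patients subjected to elder abuse".

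For the main outcome, the Statistical analysis section warns of underlying time trends and says that "both intervention status and time will be included as fixed effects in the models". It also says that the models "include cluster as random effect to determine if the anticipated effect of the model is dependent on the cluster". The paragraph on the records neither repeats nor excludes these terms.

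The design is non-randomised. Study design says that the training was to be "rolled out during four periods between September 2021 and June 2023"; Sample size says "We planned for a three-step intervention and used the discrete time decay". Some clusters were replaced during the trial, and cluster 9 became a training day open to staff from several primary care centres.

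**The concern.** A stepped wedge handles time trends by letting late clinics supply long unexposed series alongside early clinics that are already exposed. The retrieval rule gives up much of this. A clinic trained last supplies one unexposed half-year, the same as a clinic trained first, although routine records could supply more.

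The plan has reason not to presume a constant effect: it retrieves the two post windows separately, and Study design distinguishes intermediate from long-term follow-up. If the effect fades or grows, the trend adjustment can absorb part of the change. The questionnaire outcomes are all self-reported, so the record count is the one outcome that the plan describes as possibly objective.

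**Working it through.** The plan gives no sample size or precision for the record outcome, so it has no figure to reproduce. The cluster size of 10 under Sample size concerns the survey outcome and plays no part here.

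**Inputs from the documents:** three half-year windows per clinic; staggered, non-randomised training; cluster as random effect and time as fixed effect (both written for the main outcome).

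**Assumptions:** windows anchored to each clinic's own training date (the natural reading, not stated in those words); the fixed time effect applied to this model, as categorical half-years; nine clinics (the highest cluster number named); steps six months apart, either four steps with 3, 2, 2 and 2 clinics or three steps with 3 each; one count per clinic and half-year with residual variance 1. The between-clinic share of variance is not given, so 0.2, 0.5 and 0.8 are used.

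**1. Collinearity.** Let s be the clinic's step and k = -1, 0, 1 the window. Calendar half-year is t = s + k in every row. A clinic effect absorbs s, so within clinics t and k cannot be told apart.

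**2. Two separate post effects.** With a trend b per half-year and effects e1 (0-6 months) and e2 (6-12 months), each clinic gives two differences:
- second window minus first: b + e1
- third window minus second: b + e2 - e1

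That is two equations in three unknowns, the same for every clinic. With categorical half-years and clinic fixed effects, the design matrix has 9 + 5 + 2 = 16 columns and rank 15 (four steps), or 9 + 4 + 2 = 15 columns and rank 14 (three steps). Neither effect is estimable. Shifting the first-period primary care centres to December 2021 does not cure this.

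**3. One pre/post effect, clinic fixed effects.** The matrix has full rank (15/15 or 14/14), so the effect is estimable. Subtracting the second difference from the first gives what is estimated: (b + e1) - (b + e2 - e1) = 2·e1 - e2. This is right when e1 = e2. For 1 then 0.5 it is 2 - 0.5 = 1.5; for 1 then 2 it is 2 - 2 = 0. Categorical half-years give the same values.

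The standard error, in residual-SD units, is √(1.5/9) = 0.41 without a time term, √(6/9) = 0.82 with a linear trend and 0.91 with categorical half-years.

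**4. One pre/post effect, random clinic intercept, four steps.** The true 12-month averages are (1 + 0.5)/2 = 0.75 and (1 + 2)/2 = 1.5. Wider retrieval means a common start six months before the first training.

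| Between-clinic share | 1 then 0.5: planned | wider | 1 then 2: planned | wider |
|---|---|---|---|---|
| 0.2 | 0.85 | 0.86 | 1.29 | 1.27 |
| 0.5 | 0.96 | 0.91 | 1.08 | 1.18 |
| 0.8 | 1.18 | 0.95 | 0.65 | 1.11 |

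At share 0.8 the planned windows give estimates outside the range of the true effects in both cases.

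**5. Precision with wider retrieval.** With four steps, clinic-half-years rise from 9 × 3 = 27 to 3×3 + 2×4 + 2×5 + 2×6 = 39. The number of exposed ones stays at 18, so unexposed ones rise from 9 to 21. The model with two post effects and clinic fixed effects then has full rank (16/16; three steps 15/15). Variance of the pre/post effect with a random intercept:

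| Between-clinic share | Four steps: planned | wider | Three steps: planned | wider |
|---|---|---|---|---|
| 0.2 | 0.29 | 0.23 | 0.35 | 0.32 |
| 0.5 | 0.38 | 0.29 | 0.47 | 0.39 |
| 0.8 | 0.56 | 0.34 | 0.66 | 0.44 |

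The variance of the 6-12 month effect at share 0.8 with four steps falls from 1.70 to 0.59.

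**The case against.** A reader might infer that the effect cannot be separated from trend at all, or that a growing effect would be reported as none. The documents do not support either. The contrast that the plan names is pre versus post, which is estimable within clinics because training dates are staggered, provided that the effect is constant. The values 1.5 and 0 need clinic fixed effects, whereas the plan names a mixed model. With a random intercept even the model with two post effects has full rank (8/8 for four steps, 7/7 for three). At shares of 0.2 and 0.5 the wider data change the single-term estimate little. All of this stands.

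What remains is that the random intercept fills the gap by comparing levels between clinics. Those clinics were not randomised to steps and mix hospital clinics with primary care centres.

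It is also fair that the layout is assumed and that the record paragraph does not say whether time enters the model. If it does not, the collinearity does not arise, but trend goes unadjusted: a rise of 1 per half-year with no effect would give a false pre/post effect of (1 + 2)/2 = 1.5. Finally, no primary or secondary conclusion depends on this outcome.

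**Conclusion.** The point holds in this form: the planned windows cannot separate a changing effect from a secular trend within clinics. The pre/post effect is identified within clinics only under a constant effect; otherwise it leans on non-randomised comparisons between clinics. How much this matters depends on the between-clinic share, which the documents do not give. Distortion beyond the range of the true effects appears in the four-step mixed model at share 0.8, not at 0.2 or 0.5. The precision gain from wider retrieval appears in every case examined. It runs from (0.35 - 0.32)/0.35 = 9% of the variance (three steps, share 0.2) to (0.56 - 0.34)/0.56 = 39% (four steps, share 0.8).

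All figures rest on the layout assumed above and on the main-outcome time effect applying here. Severity is low to moderate, since the outcome is declared experimental.

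**What to change.** Replace the retrieval rule with: *For each participating clinic, monthly counts will be retrieved from six months before the first training in the trial until 12 months after that clinic's own training. All pre-training months count as unexposed. The model will include calendar time and estimate the 0-6 and 6-12 month effects separately.*

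Separate effects are needed because a single pre/post term stays sensitive to a changing effect even with the wider data: the table in step 4 still shows 0.86 to 0.95 against an average of 0.75, and 1.11 to 1.27 against 1.5. Monthly counts also place the clinics trained in December 2021 correctly in calendar time.

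The cost is a wider date range in the same anonymous extraction, with no added participants or procedures. Two checks come first. The recording field and the permission to extract must cover the longer period, including for replacement clusters. The plan must also say how cluster 9 is handled, since staff from several centres may have no single clinic count.
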